APPENDIX					
16.1.7 Randomization Scheme and Codes (Subject identification and treatment assigned)					
	Listing	Randomization Information	All Randomized Subjects	16.1.7.1	
16.1.9 Documentation of Statistical Methods					
	Raw output	Statistical Analysis of Change from Baseline in Multidimensional Fatigue Inventory (MFI) Domains Over Time (MMRM) (Reference: Table 14.2.2.1.2)		R Output	Yes
	Raw output	Statistical Analysis of Change from Baseline in MFI Individual Item Scores Over Time (MMRM) (Reference: Table 14.2.3.1.2)	mITT Population	R Output	Yes
	Raw output	Statistical Analysis of Change from Baseline in Quality of Life (QoL) Questions (Secondary Endpoint) Over Time (MMRM) (Reference: Table 14.2.4.1.2)	mITT Population	R Output	
	Raw output	Statistical Analysis of Change from Baseline in Quality of Life (QoL) Questions (Exploratory Endpoint) Over Time (MMRM) (Reference: Table 14.2.5.1.2)	mITT Population	R Output	
	Raw output	Statistical Analysis of Change from Baseline in Multidimensional Fatigue Inventory (MFI) Domains Over Time (MMRM) – Sex Subgroup (Reference: Table 14.2.2.1.4)	mITT Population	R Output	

Haleon Confidential

 Statistical Analysis Plan template v7.0

CSR Section	TLF	Title	Population	Template	Topline
	Raw output	Statistical Analysis of Change from Baseline in MFI Individual Item Scores Over Time (MMRM) – Sex Subgroup (Reference: Table 14.2.3.1.4)	mITT Population	R Output	
	Raw output	Statistical Analysis of Change from Baseline in Quality of Life (QoL) Questions (Secondary Endpoint) Over Time (MMRM) – Sex Subgroup (Reference: Table 14.2.4.1.4)	mITT Population	R Output	
	Raw output	Statistical Analysis of Change from Baseline in Multidimensional Fatigue Inventory (MFI) Domains Over Time (MMRM) – Age Subgroup (Reference: Table 14.2.2.1.6)	mITT Population	R Output	
	Raw output	Statistical Analysis of Change from Baseline in MFI Individual Item Scores Over Time (MMRM) – Age Subgroup (Reference: Table 14.2.3.1.6)	mITT Population	R Output	
	Raw output	Statistical Analysis of Change from Baseline in Quality of Life (QoL) Questions (Secondary Endpoint) Over Time (MMRM) – Age Subgroup (Reference: Table 14.2.4.1.6)	mITT Population	R Output	
16.2 Subject Data Listings					
16.2.1 Discontinued Subjects					
	Listing	Subject Disposition	All Randomized Subjects	16.2.1.1	---
	Listing	Subject Disposition	Non-Randomized Subjects	16.2.1.2	---
16.2.2 Protocol Deviations					

Haleon Confidential

CCI Statistical Analysis Plan template v7.0

CSR Section	TLF	Title	Population	Template	Topline
	Table	Incidence of Important Protocol Deviations	All Randomized Subjects	14.1.2	---
	Listing	Important Protocol Deviations	All Randomized Subjects	16.2.2.1	---
	Listing	All Protocol Deviations	All Randomized Subjects	16.2.2.2	---
16.2.3 Patients Excluded from the Efficacy Analysis					
	Listing	Exclusion from Analysis Population	All Randomized Subjects	16.2.3.1	---
16.2.4 Demographic Data					
	Listing	Demographic and Baseline Characteristics	All Randomized Subjects	16.2.4.1	---
	Listing	Medical History and Current Medical Conditions	All Randomized Subjects	16.2.4.2	---
	Listing	Prior Medications	Safety Population	16.2.4.3	---
	Listing	Concomitant Medications and Significant Non-Drug Therapies	Safety Population	16.2.4.4	---
16.2.5 Compliance and/or Drug Concentration Data (if available)					
	Listing	Study Product Compliance	All Randomized Subjects	16.2.5.1	---

Haleon Confidential

 Statistical Analysis Plan template v7.0

CSR Section	TLF	Title	Population	Template	Topline
16.2.6 Individual Efficacy Response Data					
	Listing	MFI Domain Scores	All Randomized Subjects	16.2.6.1	---
	Listing	MFI Individual Item Scores	All Randomized Subjects	16.2.6.2	---
	Listing	QoL Questions (Secondary Endpoint)	All Randomized Subjects	16.2.6.3	---
	Listing	QoL Questions (Exploratory Endpoint)	All Randomized Subjects	16.2.6.4	---
16.2.7 Adverse Event Listings					
	Listing	All Adverse Events	All Randomized Subjects	16.2.7.1	---
	Listing	All Adverse Events	Non Randomized Subjects	16.2.7.2	---
16.2.8 Other Listings and Listing of Laboratory Measurements, when required by regulatory authorities (if applicable)					
	---	---	---	---	---

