5.1 Schedule of Activities

The Schedule of Activities (Table 5-1) provides an overview of the subjects virtual visits, study procedures and assessments. The investigator may schedule additional (unplanned) virtual visits to conduct additional evaluations or assessments required to protect the well-being of the subject. A detailed schematic of the Schedule of Activities is located in section 9.9 Schedule of Activities Schematic.

Table 5-1 Schedule of Activities

Visit	Treatment Period					
	Pre-screening	Visit 1 Screening & Baseline	Treatment Initiation	Virtual Visit 2	Virtual Visit 3	Virtual Visit 4
Study Day	Day-7 to Day -2	Day -7 to Day -2	Day 1	Week 4 Day 28 (+5)	Week 8 Day 56 (+5)	Week 12 Day 84 (+5)
Medical/Medication History ^a	X					
Demographics ^a	X					
Informed Consent	X					
Subject ID Verification		X				
Inclusions/Exclusion Criteria ^c		X				
Eligibility Assessment		X				
MFI ^a	X			X	X	X
Supplementary QOL questionnaire ^a		X		X	X	X
Randomization		X				
Participant Training		X				
Study Product Shipped		X				
Concomitant Medication Check		X		X	X	X
Adverse Event (AE/ Serious Adverse Event)		X	X	X	X	X
Study Product Administration ^b			X (Daily through Week 12 visit)			
Participant Daily eDiary ^d			X (Daily through Week 12 visit)			
Subject Conclusion/Subject Exit from Study						X
Exit Survey ^a						X

Footnotes:

^aSubject-reported (self-reported) assessments.

Property of Haleon- Confidential

May not be used, divulged, published or otherwise disclosed without the consent of Haleon

CCI [REDACTED] Abbreviated Clinical Protocol Template v1.0

^bSubject will take the study product in the morning of each day

^cSubject will self-report pregnancy status during Visit 1

^dSubject-reported (self-reported) they took the investigational product on that day.

The virtual site may contact subjects prior to study visits, either as part of pre-screening activities or as a reminder of the approaching scheduled visit. Further details should be included in the electronic informed consent (eICF).

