5.2.5 Enrolled Subjects and Screen Failures

An enrolled subject is one who has agreed to participate in the clinical study following completion of the informed consent process and who has directly and successfully met eligibility criteria to proceed beyond the screening visit.

Screen failures are defined as subjects who consent to participate in the clinical study but are not subsequently randomized to a study group.

To ensure transparent reporting of screen failure subjects, a minimal set of screen failure information will include demography and screen failure details (e.g., withdrawal of consent, eligibility criteria, any protocol deviations and any adverse events).

Individuals who do not meet the criteria for participation in this study (screen failure) will not be re-screened.

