9.1.3 Time Period and Frequency for Collecting AE and SAE Information

All AEs, and therefore all SAEs (except from those exempt from recording, as described in section 9.1.1 and section 9.1.2) will be collected from immediately after a subject is randomised within the trial and until 2 days following the last administration of study product (or the last study procedure).

Medical occurrences that began before randomisation will be recorded in the Medical History/Current Medical Conditions section of the Electronic Case Report Form (eCRF), not the AE section.

Details recorded by the subject that meet the definition of a serious AE must be discussed with the subjects and transcribed into the SAE section of the eCRF.

All SAEs will be recorded and reported to the sponsor or designee immediately, and under no circumstance should this exceed 24 hours. The investigator will submit updated SAE data to the sponsor within 24 hours of it being available.

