4.3 Timepoints and Visit Windows

The timepoints and visits for this study are defined in the Table 1: Schedule of Activities. Any deviation from the study schedule may be reviewed on a case-by-case basis at the Blinded Data Review Meeting (BDRM) to determine whether the data should be excluded from the Per-Protocol (PP) analyses.

Table 1: Schedule of Activities

Visit	Treatment Period					
	Pre-screening	Visit 1 Screening & Baseline	Treatment Initiation	Virtual Visit 2	Virtual Visit 3	Virtual Visit 4
Study Day	Day-7 to Day -2	Day -7 to Day -2	Day 1	Week 4 Day 28 (+5)	Week 8 Day 56 (+5)	Week 12 Day 84 (+5)
Medical/Medication History ^a	X					
Demographics ^a	X					
MFI ^a	X			X	X	X
Informed Consent	X					

Haleon Confidential

CCI Statistical Analysis Plan template v7.0

Visit	Treatment Period					
	Pre-screening	Visit 1 Screening & Baseline	Treatment Initiation	Virtual Visit 2	Virtual Visit 3	Virtual Visit 4
Study Day	Day-7 to Day -2	Day -7 to Day -2	Day 1	Week 4 Day 28 (+5)	Week 8 Day 56 (+5)	Week 12 Day 84 (+5)

ID Verification		X				
Inclusions/Exclusion criteria ^c		X				
Eligibility Assessment		X				
Randomization		X				
Participant Training		X				
Study Product Shipped		X				
Supplementary QOL questionnaire		X	X	X	X	X
Concomitant Medication Check		X		X	X	X
Adverse Event (AE/Serious Adverse Event)	X	X	X	X	X	X
Study Product Administration ^b				X (Daily through Week 12 visit)		
Participant Daily eDiary ^a				X (Daily through Week 12 visit)		
Subject Conclusion/Subject Exit from Study						X

^aSubject-reported (self-reported) assessments.

^bSubject will take the study product in the morning of each day

^cSubject will self-report pregnancy status during Visit 1

5 Data Analysis

Data analysis will be performed by PPD [REDACTED], independent biostatistics consultant CCI [REDACTED], with oversight from Haleon. The statistical analysis software used will be Stata Version 18 or later (StataCorp. 2023. *Stata Statistical Software: Release 18*. College Station, TX: StataCorp LLC).

Prior to database lock and unblinding, a BDRM will be conducted in which various aspects of the trial will be discussed and agreed.

Except as described below, all listings will be produced for all randomized subjects.

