5.7 Analysis of Safety

5.7.1 Adverse Events and Serious Adverse Events

The absolute and relative frequency of adverse events (AEs) in each group will be reported, including the total number of events, the total number of patients experiencing at least one event, and the frequency of events by severity and AE category. Safety analyses will be performed on the Safety population, according to investigational product received. AEs will be regarded as ‘treatment emergent’ if they occur on or after the first use of investigational product at baseline (visit 2). In the event of a missing start date, an AE will be assumed to be ‘treatment emergent’ unless the end date is prior to starting treatment. In case of misallocation compared to the randomization schedule, TEAEs will be associated with the most recent investigational product received.

A listing of all AEs will be presented for all subjects in the Safety population with the following AE summaries (number of distinct AEs and frequency/proportion of subjects affected) presented by treatment group and overall:

- TEAEs
- TEAEs by System Organ Class (SOC) and Preferred Term (PT)
- Treatment emergent treatment related AEs by SOC and PT
- Treatment emergent treatment related serious AEs by SOC and PT

Separate listings will be presented for:

- Deaths, Severe AEs (SAE) and any AEs leading to product or study discontinuation.
- Exposure to study product

Haleon Confidential

CCI Statistical Analysis Plan template v7.0

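### Adverse-event recording has no single start point across the protocol and SAP, and the missing-start-date rule can class an event recorded before first use as treatment-emergent

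*SAP*

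**What the plan says.** Five places bear on when AE recording starts.

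- Protocol 9.1.3: AEs and serious AEs "will be collected from immediately after a subject is randomised within the trial". For anything earlier, "Medical occurrences that began before randomisation will be recorded in the Medical History/Current Medical Conditions section" of the eCRF, and the AE section is expressly ruled out.
- Protocol 5.1, Table 5-1: the row "Adverse Event (AE/ Serious Adverse Event" is marked from Visit 1 onward (five marks), and pre-screening is blank.
- SAP 4.3, Table 1: the row "Adverse Event (AE/Serious Adverse Event" is marked in all six columns, including pre-screening.
- Protocol 5.2.5: screen failures are "subjects who consent to participate in the clinical study but are not subsequently randomized" to a study group, and the minimal data kept on them include "any protocol deviations and any adverse events".
- SAP Appendix 1, 16.2.7: Listing 16.2.7.2 shows all AEs for "Non Randomized Subjects".

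Two more places govern what counts as a treatment-emergent AE (TEAE). SAP 5.7.1 and Protocol 8.3.4 both require onset on or after first use of product, and both label that moment as baseline and Visit 2. Both add that an AE with a missing start date is taken as treatment-emergent "unless the end date is prior to starting treatment".

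**The concern.** A listing of AEs in subjects never randomised cannot be filled if recording begins only after randomisation. An empty listing in the study report could be taken as an observation that nothing happened, when it would only reflect a collection rule. If staff followed the SAP schedule or Protocol 5.2.5 instead, the AE page holds events that Protocol 9.1.3 sends to medical history.

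The second issue touches the stated safety endpoint, the number of TEAEs. The missing-date rule looks only at the end date. It ignores the most direct evidence available, namely that the event was already on record before the subject used any product. Such an event would be counted against the plan's own definition of treatment-emergent.

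**Working it through.** The plan gives no figure to reproduce here, so the check compares the passages and then applies the TEAE rule case by case.

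**Step 1. What each passage implies for a subject who is never randomised**

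| Source | AE recording starts | AE record possible without randomisation? |
|---|---|---|
| Protocol 9.1.3 | After randomisation | No |
| Protocol Table 5-1 | Visit 1, the visit at which randomisation occurs | Unclear |
| Protocol 5.2.5 | Not stated; AEs kept for screen failures | Yes |
| SAP Table 1 | Pre-screening | Yes |
| SAP Listing 16.2.7.2 | Not stated; lists non-randomised subjects | Yes |

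The protocol therefore disagrees with itself (9.1.3 against 5.2.5) as well as with the SAP. SAP section 6, which lists departures from the protocol, mentions none of this. SAP 5.7.1 also places the all-AE listing on the Safety population, whereas Appendix 1 uses all randomised and non-randomised subjects.

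**Step 2. Can an event before first use reach the AE page even under Protocol 9.1.3?**

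Inputs from both schedules: randomisation at Visit 1, on day r between -7 and -2; first use on Day 1.

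- If the calendar has no Day 0, the interval is (1 - r) - 1 days: 7 days for r = -7 and 2 days for r = -2.
- If it has a Day 0, the interval is 1 - r days: 8 days for r = -7 and 3 days for r = -2.

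The documents do not say which convention applies. Either way there is a window of 2 to 8 days in which AEs are collected before any product is used. The pre-screening mark widens the exposure but does not create it.

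**Step 3. The TEAE rule applied with first use on Day 1**

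| Start | End | Classed as TEAE? |
|---|---|---|
| Day -5 | Day -3 | No |
| Day -5 | Ongoing | No |
| Missing | Day -3 | No |
| Missing | Day 4 | Yes |
| Missing | Missing or ongoing | Yes |
| Day 2 | Any | Yes, correctly |

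A pre-use event is misclassified only in the fourth and fifth rows: no start date, and no end date before first use.

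**Step 4. Who can enter the count**

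The Safety population requires at least one dose (Protocol 8.2.1, SAP 5.1.3), and the AE summaries use that population. Non-randomised subjects contribute 0 TEAEs.

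**Step 5. The anchor**

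In both schedules baseline is Visit 1, first use is Day 1, and Virtual Visit 2 is Week 4. The label attached to first use in SAP 5.7.1 and Protocol 8.3.4 fits none of these.

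**The case against.** The strongest reply is that this is housekeeping. SAP Table 1 is a reproduced schedule, SAP 2.1 sends the reader to Protocol section 5 for procedures, and the protocol's own table leaves pre-screening blank. Treating a missing onset as treatment-emergent is a conservative default, prespecified identically in both documents. Misclassification needs several things together: an event before first use, entered on the AE page, with no start date, not resolved by the edit checks and queries of Protocol 9.4.2 and 9.4.3, and with no end date before first use. Safety reporting is descriptive. Most of this stands, and it limits the point to a minor one. It does not remove the contradiction over the start of recording, and a conservative default for unknown timing is not needed when the record itself shows that the event came before first use.

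A reader might go further and make any of four inferences that the documents do not support.

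- That events in screen failures inflate the TEAE count. They cannot, because those subjects receive no dose.
- That pre-use events in general become TEAEs. Those with a known start date are excluded.
- That choosing one start of recording would cure the TEAE problem. It would not, because of the interval in Step 2.
- That about 130 subjects (430 planned for screening minus 300 enrolled) fall in the empty listing. Screen failures are those who consented, the pre-screening questionnaire comes before consent, and nothing says that all 430 consent. On the planned figures, 130 is at most an upper limit.

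**Conclusion.** The point holds as a minor one, in two separate parts. The start of AE recording is inconsistent, and under Protocol 9.1.3 Listing 16.2.7.2 is empty by rule. Independently of that, the missing-start-date rule can class an event recorded before first use as treatment-emergent, and the anchor for the definition fits neither schedule.

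The effect on results is confined to descriptive safety counts. It should not favour either arm, since randomisation spreads such events over both and the study is double-blind. Its size cannot be estimated: the documents give no rate of events before first use, of missing start dates, or of unresolved queries, and any percentage would be a guess. The conclusion assumes that the rule is programmed as written and that some start dates remain missing after data cleaning. The primary efficacy analysis is not affected.

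**What to change.** 1. Reconcile Protocol 9.1.3, Protocol 5.2.5, Protocol Table 5-1, SAP Table 1 and SAP Appendix 1 on one start of AE recording, and align the listing populations in SAP 5.7.1 and Appendix 1. If AEs were in fact collected only from randomisation, remove the pre-screening mark from SAP Table 1 and either delete Listing 16.2.7.2 or footnote it to say that these events were not collected. SAP Appendix 2 reports a decision already taken at the blind data review, so changing 9.1.3 now could not recover events that were never collected.
2. Add to the missing-date rule in SAP 5.7.1 that an event first recorded before first use of product is not treatment-emergent, unless it is recorded as worsening afterwards.
3. In SAP 5.7.1, replace the visit label on the TEAE anchor with the actual date of first use, and note the departure from Protocol 8.3.4 in SAP section 6.

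The cost is wording, one listing removed or footnoted, and one line in the TEAE derivation. No new data collection is needed. The audit trail described in Protocol 9.4.2 should show when an event was entered if the contact date is not on the AE page.

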16.4 Individual Subject Data Listings					
	NA				

Haleon Confidential

CCI Statistical Analysis Plan template v7.0

Emergen-C Core Super Orange Powder
300217

Haleon Confidential

CC [REDACTED] Statistical Analysis Plan template v7.0

Page 30 of 34

Appendix 2: Addendum (Change in treatment compliance definition)

Rationale for changes:

During the Blind Data Review, a decision was made to alter the treatment compliance definition.

- The original version used was based on virtual visit dates. However, the main outcome uses the MFI questionnaire which may have been completed on a different date to the virtual visit. Therefore, the new treatment compliance definition uses MFI completion date, rather than virtual visit date.
- The original version stated that if the virtual visit 4 MFI questionnaire is not completed, the date used as the definition will be the final virtual visit date. However, to maintain measurement over a 12-week treatment period, in the new definition, if the virtual visit 4 MFI questionnaire is not completed, the date used as the definition will be the treatment initiation date plus 84 days.
- The daily diary that was used to record treatment compliance could only be completed once per day and therefore did not capture any additional doses. No additional doses were reported as a protocol deviation. Therefore, additional doses have been removed from the treatment compliance calculation.

Original version of treatment compliance section:

Treatment compliance will be assessed daily during the 12-week treatment period – the end of the treatment period will be defined as the completion of the last virtual visit 4 MFI questionnaire. If the virtual visit 4 MFI questionnaire is not completed, the date used as the definition will be the final virtual visit date. Both definitions have an acceptable window of +/- 5 days. Compliance will be analyzed descriptively by reporting the absolute and relative frequency of subjects with 80% compliance to treatment per block of 4 treatment weeks and overall, for

Haleon Confidential

CCI [REDACTED] Statistical Analysis Plan template v7.0

each group. A compliance score will be calculated for each subject by dividing the number of days the allocated treatment was taken by the number of days the treatment was allocated. The compliance score will be summarized for each group and compared between groups.

Additional information on both number of doses taken, number of expected doses taken, dose compliance, number of missed doses and number of additional doses presented both in Table 14.2.1.1 and Listing 16.2.5.1 where:

- Number of doses taken for ‘Visit X – Visit Y’ is defined as: [(date of Visit Y – date of Visit X) – number of missed doses between Visit X and Visit Y + number of additional doses between Visit X and Visit Y] by visit, and [(date of final visit – date of baseline visit) – number of missed dose + number of additional dose] for overall.
- Dose compliance (%) = [100 x (Number of doses taken / Expected number of dose)].
- Number of expected dose for ‘Visit X – Visit Y’ is defined as: [(date of Visit Y - date of Visit X)] by visit, and [(date of Final visit – date of Baseline visit)] for overall.

Final visit in the above definitions is the date the subject completed their week 12 MFI questionnaire (or the final virtual visit if not completed).

Compliance will be tabulated using absolute and relative frequencies, and compliance score using mean, standard deviation, minimum and maximum values and median (see Table 14.2.1.1 and Listing 16.2.5.1).

New version of treatment compliance section:

Haleon Confidential

CC Statistical Analysis Plan template v7.0

Treatment compliance will be assessed daily during the 12-week treatment period – the end of the treatment period will be defined as the completion of the last virtual visit 4 MFI questionnaire. If the virtual visit 4 MFI questionnaire is not completed, the date used as the definition will be the treatment initiation date plus 84 days. Both definitions have an acceptable window of +/- 5 days. Compliance will be analyzed descriptively by reporting the absolute and relative frequency of subjects with 80% compliance to treatment per block of 4 treatment weeks and overall, for each group. A compliance score will be calculated for each subject by dividing the number of days the allocated treatment was taken by the number of days the treatment was allocated. The compliance score will be summarized for each group and compared between groups.

Additional information on number of doses taken, number of missed doses, number of expected doses, and dose compliance will be presented both in Table 14.2.1.1 and Listing 16.2.5.1 where:

- Number of doses taken is defined as:
 - Overall: Number of times daily diary indicates a dose was taken between treatment initiation and Week 12 MFI completion date. If the virtual visit 4 MFI questionnaire is not completed, the date used as the definition will be the treatment initiation date plus 84 days.
 - Treatment Start to Week 4: Number of times daily diary indicates a dose was taken between treatment initiation and Week 4 MFI completion date. If the virtual visit 2 MFI questionnaire is not completed, the date used as the definition will be the treatment initiation date plus 28 days.
 - Week 4 to Week 8: Number of times daily diary indicates a dose was taken between Week 4 MFI completion date and Week 8 MFI completion date. If the virtual visit 3 MFI questionnaire is not completed, the date used as the definition will be the treatment initiation date plus 56 days.

- Week 8 to Week 12: Number of times daily diary indicates a dose was taken between Week 8 MFI completion date and Week 12 MFI completion date. If the virtual visit 4 MFI questionnaire is not completed, the date used as the definition will be the treatment initiation date plus 84 days.
- Number of expected doses is defined as:
 - Overall: Week 12 MFI Completion Date - Treatment Start Date.
 - Treatment Start to Week 4: Week 4 MFI Completion Date - Treatment Start Date.
 - Week 4 to Week 8: Week 8 MFI Completion Date – Week 4 MFI Completion Date.
 - Week 8 to Week 12: Week 12 MFI Completion Date – Week 8 MFI Completion Date.
- Number of missed doses is defined as number of expected doses – number of actual doses taken for each time period.
- Dose compliance (%) = $[100 \times (\text{Number of doses taken} / \text{Expected number of dose})]$.

Compliance will be tabulated using absolute and relative frequencies, and compliance score using mean, standard deviation, minimum and maximum values and median (see Table 14.2.1.1 and Listing 16.2.5.1).

In section 5.1.4.2, reference to total MFI domain removed as not applicable to the endpoints (typo from draft version).
